11.0 TOXICITIES/SIDE EFFECTS

- 11.1 PET Scanning. Potential risks to the patient are small, and present more of an inconvenience (multiple scans on consecutive days). The GE Advance tomograph has a large bore (92.7 cm in diameter) to accommodate the whole body and the environment is much less confining than the head cage of the General Electric Signa 1.5 Tesla MR tomograph. For the first 20 patients, the length of time in the PET scanner will be ~45 min for the [11C-methionine head scan; for the [18F]-FACBC scan, an initial scanning period of the head will be ~45 min, followed by ~45 min for each of the up to three subsequent body scan periods (maximum total time in the scanner for the [18F]-FACBC imaging series will be ~180 minutes). The last 10 patients will be scanned for a maximum of ~90 minutes (an initial [18F]-FACBC scanning period of the head will be ~45 min, followed by a ~45 min body scan). This is long and could produce some discomfort because movement and changes of position will be discouraged. However, there will be substantial breaks between each of the [18F]-FACBC imaging sequences where the patient will come out of the scanner. Many studies on patients have been performed for this length of time and longer.
- 11.2 Radiation Exposure. The radiation exposure from diagnostic 3-[18F]-FACBC or [11C-methyl]-L-methionine PET studies is expected to be within acceptable limits as established by FDA Guidelines (Code of Federal Regulations, Section 361.1). Dosimetry estimates of [11C-methyl]-L-methionine to critical organs have been reported [16 and Appendix B]. Preliminary measurements of 3-[18F]-FACBC dosimetry performed Emory have been reported [11 and Appendix B] and will be extended by results obtained in this study.
- 11.3 The dosimetry estimates in Appendices B have led us to select a conservative 185 MBq (5 mCi) dose of [11C-methyl]-L-methionine and a 370 MBq (10 mCi) dose of 3-[18F]-FACBC for this study. This will maintain the radioactivity exposure to all normal tissue (including whole body, blood forming organs and gonads) well below the annual radiation dose limit of 5 cSv established by the FDA (Code of Federal Regulations, Section 361.1) (see Appendix B). In the event that our measurements and dosimetry estimates for 3-[18F]-FACBC exceed the annual radiation dose limit of 5 cSv established by the FDA, we will reduce the administered dose of 3-[18F]-FACBC to insure that the annual radiation dose limit of 5 cSv is not exceeded.

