4.0 STUDY DESIGN

- 4.1 The first set of 20 patients will consent to two PET studies. One study will involve the i.v. administration of a fluorine-18 labeled amino acid analogue, 3-fluoro-aminocyclobutane carboxylic acid (3-[18F]-FACBC) with sequential brain and body PET imaging. The second study will involve i.v. administration of [11C-methyl]-L-methionine for a head imaging study only. An additional set of 10 patients will consent to one type of PET study which will involve administration of [18F]-FACBC only for one brain scan and one body scan.
- 4.2 ~~All~~The first set of 20 patients will first undergo a [11C-methyl]-L-methionine PET study. Whenever possible, approximately two hours later, the same patient will undergo the [18F]-FACBC PET study.
- 4.3 For the first 20 patients, we will attempt to complete both studies on the same day; if this is not possible, the two PET studies will be completed within 1 week of each other.

- 4.4 The 3-[18F]-FACBC and [11C-methyl]-L-methionine PET images will be digitally registered to each other and to corresponding contrast enhanced and FLAIR MR images (from the most recent MR study obtained as part of the patient's standard medical care). Region of interest (ROI) measurements of 3-[18F]-FACBC and [11C-methyl]-L-methionine activity in tumor and remote brain tissue will be obtained from the two data sets and paired comparisons will be performed.
- 4.5 The study will also provide data to determine body and critical organ radioactivity exposure (dosimetry) following 3-[18F]-FACBC administration. These calculations will be based on the biodistribution and clearance of radioactivity from the tissues and organs of the body as determined by sequential PET imaging.
- 4.6 Look for potential correlations between the MR and PET scan results obtained from those patients enrolled to 03-028 and the patients' past medical treatment, as well as the patients' subsequent medical treatment, progression of the tumor and survival. _

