9.0 TREATMENT/INTERVENTION PLAN

- 9.1 All subjects will be pre-registered at MSKCC and will have signed the consent form prior to participation in this study.
- 9.2 The morning of the PET imaging studies, all patients will be asked to avoid high protein foods (meat, fish, poultry, cheese, eggs, beans and nuts) and to record the types and servings of the foods they eat. Some patients may also be asked to avoid high protein foods the day prior to imaging. These same patients will also be asked to refrain from eating lunch on the day of the study to reduce muscle uptake of the FACBC. All patients will also be urged to drink several glasses of water to attain good hydration and urine output. Patients will be placed comfortably on the couch and positioned in the GE Advance PET scanner. The first 20 patients will first receive 185 MBq (5 mCi) of [11C-methyl]-L-methionine by i.v. infusion over approximately 1 minute. Whenever possible, approximately 1.5 to 2 hours later, the same patient will receive 370 MBq (10 mCi) [18F]-FACBC by i.v. infusion over approximately 1 minute. In cases where both studies cannot be obtained on the same day, they will be obtained within one week of each other.
- 9.3 For the first 20 patients, the [11C-methyl]-L-methionine study will involve a 45-minute emission dynamic scan of the head. Previous studies have shown that [11C-methyl]-L-methionine accumulation in tumor and brain tends to reach a plateau value within 15-30 minutes following administration. The [18F]-FACBC study will involve a 45-minute emission dynamic scan of the head to obtain kinetic information on tumor uptake for modeling. After the initial dynamic scan, the patient will void completely; the volume of urine will be recorded and a urine sample will be assayed for urine radioactivity. Up to three [18F]-FACBC body scans will be performed following the completion of the dynamic scan to obtain data for calculating body and organ specific dosimetry. The last 10 patients will undergo a [18F]-FACBC 45-minute emission dynamic scan of the head followed by one body scan.

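### Minor: the dose-reduction trigger in section 11.3 tests the FACBC dose alone against 5 cSv, although the same section holds the two tracers together to that limit

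*Combined protocol and SAP*

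**What the plan says.** Section 11.3 (Toxicities/Side Effects) makes three statements in sequence.

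1. It selects the activities as a pair: "a conservative 185 MBq (5 mCi) dose of [11C-methyl]-L-methionine and a 370 MBq (10 mCi) dose of 3-[18F]-FACBC for this study".
2. It gives an assurance about that selection, with 5 cSv as the yardstick: "This will maintain the radioactivity exposure to all normal tissue (including whole body, blood forming organs and gonads) well below the annual radiation dose".
3. It adds a fallback, whose condition is "In the event that our measurements and dosimetry estimates for 3-[18F]-FACBC exceed the annual radiation dose limit of 5 cSv". The action is to lower the FACBC activity, and the stated purpose is "to insure that the annual radiation dose limit of 5 cSv is not exceeded".

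On who receives both tracers, section 4.1 says: "The first set of 20 patients will consent to two PET studies". The further 10 patients receive FACBC only. Section 9.2 fixes the order: "The first 20 patients will first receive 185 MBq (5 mCi) of [11C-methyl]-L-methionine by i.v. infusion over approximately 1 minute". FACBC follows on the same day where possible; otherwise, "In cases where both studies cannot be obtained on the same day, they will be obtained within one week of each other".

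On methionine dose, section 11.2 says: "Dosimetry estimates of [11C-methyl]-L-methionine to critical organs have been reported", citing a publication and Appendix B. Section 10.6 plans new dosimetry for FACBC only.

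**The concern.** The assurance in 11.3 concerns exposure from two activities, while the safeguard behind it tests the exposure from one. The limit is an annual one, and a two-tracer patient receives both doses within a week at most, so both count in the same year. If an organ's FACBC dose came in just under 5 cSv, the methionine dose already received could take the total above the limit without prompting any reduction.

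What is at stake is whether a safety contingency does what it says it is for. No endpoint, analysis or starting activity depends on it. The contingency still deserves exact wording, because it exists for the case where expectations fail: 11.2 describes the existing FACBC dosimetry as preliminary, and objective 2.2 is to measure it.

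**Working it through.** There is no sample size, power or precision figure to reproduce here. The 5 cSv limit is a constant that 11.3 quotes. The check is to compare the trigger as written with a trigger on the total.

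**Inputs**

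- Limit: 5 cSv per year, for all normal tissue (11.3).
- Planned FACBC activity: 370 MBq; planned methionine activity: 185 MBq (9.2, 11.3).
- F: FACBC dose to a given organ at 370 MBq, in cSv. To be estimated in the study (10.6).
- M: methionine dose to the same organ at 185 MBq, in cSv. The protocol cites estimates, but the visible text gives no values, so M stays a symbol, with 0 < M < 5.
- Patients: 20 planned for both tracers, 10 for FACBC only, 30 in all (4.1, 6.1).

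**When each rule fires**

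- As written: F > 5.
- On the total: F + M > 5, that is, F > 5 - M.
- Missed by the written rule: 5 - M < F <= 5. This window is M wide.
- Largest total inside the window: at F = 5, the total is 5 + M.

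The window exists for any M above zero. How wide it is, and whether any organ could fall in it, cannot be computed from the document.

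**Which activity can be adjusted**

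Methionine is given first, so M has already been received when FACBC is injected. FACBC is the only activity left to lower. The action in 11.3 is therefore aimed at the right tracer; only the condition is incomplete.

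**Size of the reduction under a rule on the total**

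Organ dose is proportional to administered activity. To bring the total to 5, the FACBC activity must be

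370 x (5 - M)/F MBq,

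which is a fractional cut of 1 - (5 - M)/F = (F + M - 5)/F. Inside the window this rises from 0 at F = 5 - M to M/5 at F = 5. The extra cut is therefore at most M/5 when F is 5 cSv or less.

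**Who could be affected**

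Two-tracer patients are 20/30 = 67% of planned enrolment. That is a ceiling. The FACBC estimates come from patients already scanned, and a reduction can help only those not yet dosed. The protocol gives no time at which the estimates are reviewed, so the number who could benefit cannot be stated. The 10 FACBC-only patients have M = 0 from this study, and for them the written trigger is complete.

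**The case against.** Five arguments deserve weight.

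*FACBC is the natural tracer to name.* It is the one being measured and the one studied under RDRC guidelines, while methionine is in the hospital formulary and in clinical use (Summary; 3.5). This explains the drafting. It does not remove the mismatch, because 11.3 itself names both activities and claims one resulting exposure. A reader might go further and infer that 11.2 applies the same 5 cSv limit to methionine. It does not: it refers to studies with one tracer or the other, speaks of acceptable FDA limits, and gives no 5 cSv figure. The point rests on 11.3 alone.

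*The purpose clause already implies the total.* A team guided by that clause might well count methionine. But the clause governs how far the activity is reduced, and the condition decides whether a reduction starts. If the total was intended, the condition should say so.

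*Section 10.6 also plans a worst-case calculation with no biological clearance.* If that estimate fed the trigger, the rule would fire earlier and might offset some or all of M. The protocol does not say which estimate the trigger uses, so this cannot be relied on as the remedy.

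*Appendix B may already give combined figures.* It is not in the public text, and its absence is no fault of the plan. Combined figures would support the starting activities. They would not change the wording of the trigger.

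*An overrun is improbable.* This stands. A reader might infer that two-tracer patients are likely to exceed 5 cSv, or that the planned activities are unsafe. Nothing in the document supports either: it expects exposure well below the limit, and no organ dose is given that would suggest otherwise.

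**Conclusion.** The point holds as a minor one. Read literally, the trigger in 11.3 does not fully serve its stated purpose in patients who receive both tracers: it is silent for FACBC organ doses between 5 - M and 5 cSv, where totals of up to 5 + M cSv would pass.

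This assumes that the limit in 11.3 applies to the sum of the two tracers, which is how the assurance reads, and that M is above zero in the organ concerned. No numerical size can be put on the window. It would be tempting to say that 20 patients lack protection; the document supports only that up to 20 are planned for both tracers and that some smaller, unknown number could benefit. This is a low-probability contingency and is worth correcting mainly because doing so is cheap.

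**What to change.** Reword only the trigger in 11.3, for example:

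> For patients receiving both tracers, the 3-[18F]-FACBC activity will be reduced if, for any organ with a reported [11C-methyl]-L-methionine estimate, the 3-[18F]-FACBC dose plus the cited methionine dose at 185 MBq exceeds 5 cSv; the reduction will bring the sum to no more than 5 cSv. For other organs, and for patients receiving 3-[18F]-FACBC only, the same rule applies to the 3-[18F]-FACBC dose alone.

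The restriction to organs with a reported estimate is needed because 11.2 refers to methionine estimates for critical organs, and these may not match the FACBC organ list.

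The cost is a sentence or two of text and a sum per organ, using methionine dosimetry the protocol already cites and FACBC estimates it already plans. No scans, samples or analyses are added, and the starting activities stay as they are. The downside is that, near the limit, FACBC activity in two-tracer patients is cut somewhat earlier, with some loss of image counts. That cut arises only when the sum would otherwise exceed 5 cSv.

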12.0 CRITERIA FOR THERAPEUTIC RESPONSE/OUT COME ASSESSMENT

Evaluation of therapy is not the focus of this proposal.

13.0 CRITERIA FOR REMOVAL FROM STUDY

- 13.1 If the patient is no longer able to participate in the protocol and imaging schedule.
- 13.2 If the patient's primary physician and the PI consider that further participation in the protocol would not be in the best interest of the patient.
- 13.3 If at any time the patient is found to be ineligible for the protocol as designated in the section on Criteria for Patient/Subject Eligibility (e.g., a change in diagnosis), the patient will be removed from the study.

14.0 BIOSTATISTICS

- 14.1 This is a pilot study involving only ~~20~~ 30 patients initially. Basic measurements (biodistribution, clearance, radioactivity exposure) will be summarized as means, ranges and standard deviations.
- 14.2 Published data in humans and our own prior laboratory experience indicate that statistical analyses of measurements of the type we propose to study would benefit from first applying a logarithmic transformation. For example, cumulated activities per unit of administered activity in Table 3 of [17] had nearly constant coefficients of variation (CoV) within subgroups of organs: 24.7% average CoV for brain, heart, kidneys and liver and 11.9% average CoV for lungs, pancreas and spleen. (Note that we corrected the published calculations of standard deviations to the unbiased estimate using divisor = n-1.) Our own preliminary animal data had an average CoV of 24.4%. This suggests that mean organ values could be estimated with 95% confidence to within +/- 16% from a sample of size 10, and within +/- 11% from a sample of size 20.
- 14.3 Randomization of the sequence of studies will not be performed because of our objective to perform both studies on the same day; the [11C-methyl]-L-methionine study must be performed first because 11-C has the shorter physical half-life (20 minutes vs. 110 min for 18-F). A 3 or more hour interval will separate the [11C-methyl]-L-methionine and 3-[18F]-FACBC studies to allow for near complete 11-C decay.
- 14.4 Data may be compared to FDG scans, when available.

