- 9.4 A venous catheter will be placed in a superficial hand or arm vein for administration of the radiopharmaceuticals. A second venous catheter will be placed in the opposite hand or arm for "warmed arterialized" venous blood sampling. For the first 20 patients, a blood sample will be obtained just prior to the injection of [11C-methyl]-L-methionine and [18F]-FACBC to measure plasma amino acid concentration at the time of each study. Sequential blood samples will be obtained following [18F]-FACBC infusion and assayed for whole blood and plasma radioactivity, to check for radiolabeled metabolites by HPLC, and to measure plasma amino acid concentration at the time of the study. All catheters will be removed at the end of the day.

- 9.5 After the [18F]-FACBC head scan and ~10-15 min break period, patients will be placed comfortably on the couch and positioned in the GE Advance PET scanner for sequential body imaging. The total time in the scanner for each imaging sequence will be up to 45 minutes. For the first 20 patients, this sequence of scans will be repeated a maximum of three times over a four hour post injection period (approximately two 18-F half lives). The first body scan sequence will commence ~60 min after [18F]-FACBC injection. The second and third sequences will commence at ~2 and ~3 hours post-injection of [18F]-FACBC, respectively, with a break between scans. During the intervals between scans, the patient will come out of the scanner, exercise and will be asked to void completely. To assist correct re-alignment in the scanner for repeat scans, the patient's skin will be "marked" to identify the plane defined by the PET laser during the first scan set. On the second and third scans, the technologist will position each patient field of view so as to align the laser with the skin markings.
- 9.6 Venous blood will be sampled before the methionine and FACBC scans to measure plasma amino acid concentrations. Blood samples (1/2 teaspoon per sample) will be drawn during the FACBC scans to measure the radioactivity level in your blood. Total blood sampled for the two PET studies will be less than 6 tablespoons (less than 90 ml). Whole blood and plasma will be assayed for radioactivity and for radiolabeled metabolites by HPLC.

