- 10.4 The second level of analysis will be quantitative. Volumes of interest (VOI) will be drawn on the lesions that are positive on the 3-[18F]-FACBC scan; VOI's on remote normal white and gray-matter regions of the brain will also be drawn. The mean of the voxel values within each VOI will be determined for each of the dynamic frames of the 3-[18F]-FACBC study. Profiles will be generated in units of: 1) standard uptake value [$SUV = (\% \text{ dose/g}) * \text{body weight}$] versus time, and 2) the brain tumor-to-gray or white matter ratio versus time. These curves will be evaluated to determine a single, near "optimal" tumor imaging time, for each of the patients. The criteria used in making this assessment will be target to background contrast, robustness (i.e. time insensitivity) and image noise level. The SUV and ratio values at this "optimal" time point will then be compared to similar SUV and lesion to background values determined for the corresponding location within the [11C]-methionine scan..
- 10.5 Radiolabeled metabolites of 3-[18F]-FACBC, if any, in plasma and urine will be assayed by HPLC and % parent compound vs. time profiles will be constructed for plasma and urine, and compared to the tissue radioactivity concentration vs. time profiles calculated above and used for calculating the kinetic parameters.
- 10.6 The absorbed tissue radioactivity dose estimates for 3-[18F]-FACBC will be calculated in the standard manner. Attenuation corrected PET images provide information for the tumor and organ activities directly in units of activity per cubic centimeter. Regions of interest will be drawn within identified normal organs e.g. brain, lung, liver, bladder etc. This data will be plotted versus time post injection and used for determining organ residence times. These organ residence times will be entered into MIRDOSE for determination of the organ dosimetry. MIRDOSE is a personal computer software package for internal dose assessment from tracers used in nuclear medicine [13]. This program calculates the radiation dose to each organ from the activity residing within that organ, as well as the contribution of the penetrating photon emissions from other body organs accumulating significant levels of radioactivity, according to the methodology laid out by the Medical Internal Radiation Dose (MIRD) Committee [14] (MIRD PRIMER 1988).

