The plasma and urine radioactivity concentration data (nCi/cc) will be plotted vs. time after injection. The integral of activity-time curve will be calculated from zero to infinity and multiplied by the equilibrium dose constant for 18F to obtain the absorbed dose to blood. The dose to the bladder wall will be determined using the dynamic bladder model of Cloutier et al. [15], as implemented in MIRDOSE using measured clearance data from urine samples.

The dose estimates described above incorporate estimates of the biological clearance of the tracer. Companion calculations will also be performed using the assumption of no biological clearance, i.e. only physical decay from the organ maximum. This is a

conservative “worst case” scenario and does not depend on the accuracy of the organ clearance fits.

- 10.7 Look for potential correlations between the MR and PET scan results obtained from those patients enrolled to 03-028 and the patients’ past medical treatment, as well as the patients’ subsequent medical treatment, progression of the tumor and survival.

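### Do the symmetric precision figures of ±16% (n=10) and ±11% (n=20) in section 14.2 understate the upper 95% limit?

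*Combined protocol and SAP*

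**What the plan says.** Section 14.2 (Biostatistics) states that analyses of measurements of this type "would benefit from first applying a logarithmic transformation". In support it cites, from a published human study, "24.7% average CoV for brain, heart, kidneys and liver and 11.9% average CoV for lungs, pancreas and spleen", and adds: "Our own preliminary animal data had an average CoV of 24.4" per cent. From these it concludes that "mean organ values could be estimated with 95% confidence to within +/- 16% from a sample of size 10, and within +/- 11" per cent from a sample of 20. It names neither the scale nor the quantile behind the two figures.

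Section 14.1 calls the study a pilot and plans to summarise the basic measurements by means, ranges and standard deviations. Section 9.5 limits repeated body scanning to the first 20 patients: "For the first 20 patients, this sequence of scans will be repeated a maximum of three times over a four hour post injection period".

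**The concern.** Three features of section 14.2 invite the doubt. It recommends the log scale, where a back-transformed interval reaches further above the estimate than below it, yet it reports one symmetric figure per sample size. The standard deviation will be estimated from only 10 or 20 patients, which normally calls for a t quantile. And the text does not say how the figures were obtained.

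With a t quantile on the log scale, 16 and 11 match the lower limits only, and the upper limits are about 3 points wider at n=10 and 1 point wider at n=20. If that were the right standard, the protocol's only precision statement would be too favourable on its upper side. That is the less conservative side for the organ values behind the dosimetry aim (section 2.2), and the results are meant to support an IND application (section 2.3).

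**Working it through.** **Inputs.** All are from section 14.2: CoV 24.4% (animal data) and 24.7% (brain, heart, kidneys, liver); n = 10 and 20; 95% confidence; log scale. Lognormal data are assumed.

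**Step 1: log-scale standard deviation.** s = √ln(1 + CoV²), which gives 0.2405 for CoV 0.244 and 0.2434 for CoV 0.247.

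**Step 2: reproduce the stated figures.** With the CoV taken as given, the limits are exp(±1.96·s/√n) − 1. For CoV 0.244 and n=10, the exponent is 1.96 × 0.2405/√10 = 0.149, and exp(0.149) − 1 = 16.1%. In full:

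| CoV | n | Upper | Lower | Stated |
|---|---|---|---|---|
| 24.4% | 10 | +16.1% | -13.9% | ±16% |
| 24.7% | 10 | +16.3% | -14.0% | ±16% |
| 24.4% | 20 | +11.1% | -10.0% | ±11% |
| 24.7% | 20 | +11.3% | -10.1% | ±11% |

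The upper limit, which is the wider one, rounds to the stated figure in every row, and the lower limit lies inside it. The raw scale does not reproduce the n=10 figure: a normal quantile gives 15.1% to 15.3% and a t quantile 17.5% to 17.7%. The normal-quantile log calculation is therefore the reading on which a single symmetric figure holds for both sides.

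**Step 3: the t-based alternative.** With t = 2.262 (n=10) and 2.093 (n=20), the limits are +18.8 to +19.0/-15.8 to -16.0%, and +11.9 to +12.1/-10.6 to -10.8%. This arithmetic is correct, but it describes the interval that would be reported if the observed SD equalled the planning value.

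**Step 4: is the sentence true as written?** It is a planning statement about how close the estimate will be to the true value at the assumed CoV. For a fixed band ±d, the probability is Φ(ln(1+d)·√n/s) − Φ(ln(1−d)·√n/s).

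- n=10, d=0.16: for CoV 0.244 the arguments are 1.95 and -2.29, giving 96.4%. For CoV 0.247 the result is 96.1%.
- n=20, d=0.11: 95.9% and 95.6%.

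Simulated lognormal samples at the two CoVs agree:

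| Mean used | n=10, within 16% | n=20, within 11% |
|---|---|---|
| Geometric | 96.1–96.3% | 95.7–95.9% |
| Arithmetic | 96.0–96.2% | 95.4–95.7% |

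All exceed 95%, so the statement holds for either kind of mean.

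**Step 5: where a shortfall seems to appear.** Replacing Φ in Step 4 by the t distribution gives 93.2% to 93.5% (n=10) and 94.2% to 94.5% (n=20). That is not the coverage of the band: a fixed band contains no estimated SD, so at the assumed CoV the normal calculation applies.

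**Step 6: the less variable organs.** For CoV 11.9%, even the t-based limits are only +8.9/-8.1% (n=10) and +5.7/-5.4% (n=20), well inside the stated figures.

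**The case for a change.** The best counter-argument is that the trial will not know its SD. Section 14.1 plans to report standard deviations from the sample, and section 14.2 takes care to correct published SDs to the n-1 divisor, so a known-SD calculation in the same paragraph looks inconsistent. An interval built with 1.96 and an estimated SD covers 91.8% at n=10 and 93.5% at n=20.

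This is right about intervals computed from the data, and those should use t. The protocol does not propose to compute them with 1.96, however. Section 14.2 projects precision from an assumed CoV, and for that purpose the normal quantile is ordinary practice. The t-based replacement is itself a plug-in figure: with the SD estimated at n=10, the upper limit would vary between about +10% and +28 to 29% across samples (2.5th to 97.5th percentile), with a median near +18%. The CoV is also uncertain. It comes from animal data and a cited human study of another tracer (FDG), and the upper t limits would meet the stated figures at a CoV of 21.0% (n=10) or 22.6% (n=20). A difference of 1 to 3 points is small beside either.

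It is also true that section 14.2 leaves its scale and quantile unstated. Naming them would help a reader but would change no result.

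A related worry is that organ residence times fitted from serial body scans cannot draw on all 30 patients. That does not affect these figures, because the larger sample size in section 14.2 is already 20, the number planned for serial scanning.

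**Conclusion.** The concern does not hold. The ±16% and ±11% in section 14.2 reproduce on the log scale it recommends, bound both sides to rounding, and are met with slightly more than 95% probability at the CoVs it cites (about 96% at n=10, 95.4% to 95.9% at n=20). This rests on lognormal data and on a true CoV of 24.4% to 24.7%; a larger true CoV would widen the limits under any quantile. The t-based limits of about +19/-16% and +12/-11% are a different and equally provisional convention, not a correction. No sample size, decision rule or planned summary depends on the choice, and the dose-reduction provision in section 11.3 does not refer to these figures.
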